### 10.3. Efficacy analysis

Name of data	Derivation and calculation method
Level of overall improvement	Description of level of overall improvement in the survey sheet (assessment provided by attending physician) should be employed.
Clinical improvement	Patients with the level of improvement in endoscopy findings in the survey sheet of “2. shrinkage” or lower and comprehensive evaluation of gastrointestinal symptoms in the survey sheet of “1” or lower (0, 1) are assessed as patients with clinical improvement.
Complete remission	Patients with the level of improvement in endoscopy findings in the survey sheet of “1. remission or scar” and comprehensive evaluation of gastrointestinal symptoms in the survey sheet of “0” are assessed as patients with complete remission.
Improvement in gastrointestinal symptoms (abdominal pain, diarrhoea, other gastrointestinal symptoms)	If comprehensive evaluation of gastrointestinal symptoms or evaluation of each gastrointestinal symptom differs by 1 point or higher compared to those at the start of the administration of this drug (points of evaluation at the start of administration - those at each evaluation $\geq$ 1), patients are assessed as those who obtained improvement.

Name of data	Derivation and calculation method
Level of improvement in endoscopy findings	Description in “level of improvement in ulcer with the maximum diameter” in the level of endoscopy findings in the survey sheet should be employed.
Main symptoms and accessory symptoms of Behcet disease	Description in evaluations for each main and accessory symptom in efficacy evaluation in the survey sheet should be employed. “0” should be defined as “no symptom”, “1,2,3” should be defined as “there are any symptoms”, unknown or not described data should be defined as “unknown/not described”
CRP	Measurement in the survey sheet should be employed. If measurement is undetectable, the measurement should be deemed as undetectable limit.

## 11. Method of dividing hierarchy of data

data	Method of dividing hierarchy
Dosage and administration	160mg→80mg→40mg/2 weeks, no changes thereafter 160mg→80mg→40mg/2 weeks, and 160mg or 80mg is administered at least once thereafter 160mg, and not administered thereafter 160mg→80mg, and not administered thereafter 80mg, and not administered thereafter 40mg, and not administered thereafter others
the number of administrations	at least once and less than 4 times at least 4 times and less than 12 times at least 12 times and less than 26 times at least 26 times and less than 39 times at least 39 times and less than 52 times at least 52 times and less than 65 times at least 65 times and less than 78 times at least 78 times
Total dose	lower than 500mg at least 500mg and lower than 1000mg at least 1000mg and lower than 2000mg, at least 2000mg and lower than 3000mg at least 3000mg unknown
Mean daily dose	lower than 40 mg at least 40 mg and lower than 60 mg at least 60 mg and lower than 80 mg at least 80 mg and lower than 100 mg at least 100 mg unknown

data	Method of dividing hierarchy
Administration duration	at least 0 week and shorter than 4 weeks (1-28 days) at least 4 week and shorter than 12 weeks (29-84 days) at least 12 weeks and shorter than 24 weeks (85-168 days) at least 24 weeks and shorter than 52 weeks (169-364 days) at least 52 weeks and shorter than 104 weeks (365-728 days) at least 104 week and shorter than 156 weeks (729-1093 days) unknown * When the start date of the administration is defined as 1
Reasons for discontinuation	Occurrence of adverse events, insufficient effect, patient's request, not visiting, others, multiple reasons, unknown, and not described
Sex	male, female, unknown, not described
Pregnancy/lactation	Without pregnancy/lactation, during pregnancy, during lactation, unknown, not described
Race	Japanese, other Asians, others, unknown, not described
Age (years)	Younger than 15 years, 15 years or older and younger than 65 years, 65 years or older, unknown/not described
Body weight (kg)	Lower than 30, 30 or higher and lower than 40, 40 or higher and lower than 50m, 50 or higher and lower than 60, 60 or higher, unknown/not described
Body height (cm)	Lower than 140, 140 or higher and lower than 150, 150 or higher and lower than 160, 160 or higher and lower than 170, 170 or higher and lower than 180, 180 or higher and lower than 190, 190 or higher, unknown/not described
BMI	Younger than 18.5 years, 18.5 years or older and younger than 25 years, 25 years or older and younger than 30 years, 30 years or older, unknown
Smoking habit	Absent, present, unknown, not described
Disease duration (years)	Shorter than 2, 2 or longer and shorter than 5, 5 or longer and shorter than 10, 10 or longer, unknown/not described
Reasons for use	Gastro-intestinal Behcet disease, other conditions, unknown, not described
Diagnostic classifications of Behcet disease	Complete type, incomplete type, suspected, others, unknown/not described
Main symptoms of Behcet disease	Recurrent oral mucosa aphthous ulcer, cutaneous symptoms, eye symptoms, ulcer of vulva
Evaluation of main symptoms of Bechet disease	0,1,2,3 Recurrent oral mucosa aphthous ulcer Cutaneous symptoms (erythema nodosum, subcutaneous phlebitis, folliculitis-like skin eruption, acne-like skin eruption) Ulcer of vulva Eye symptoms
Presence or absence of eye symptoms of	There is no symptom: Point for evaluation of main symptoms of Bechet disease is 0

data	Method of dividing hierarchy
Bechet disease	There are any symptoms: Points for evaluation of main symptoms of Bechet disease are 1,2,3 Unknown/not described: Other than above situations
Accessory symptoms of Bechet disease	Arthritis without deformity or rigidity, epididymitis, gastrointestinal lesions characterized by ulcer of ileocecum, vascular lesion, moderate or higher degree central nervous lesion
Presence or absence of accessory symptoms of Bechet disease	There are any symptoms: there are check marks in boxes for each accessory symptom There is no symptom: Other than above
History of allergy	Absent, present, unknown, not described
Tuberculin test or IGRA test	Not implemented, implemented, unknown, not described
HBs antigen	Not implemented, implemented, unknown, not described
HBs antibody	Not implemented, implemented, unknown, not described
HBc antibody	Not implemented, implemented, unknown, not described
HBV-DNA quantitative	Not implemented, implemented, unknown, not described
Complications	Absent, present, unknown, not described
Detailed classification of complications	Liver disorder, renal disorder, circulatory disorder, blood disorder, respiratory disorder, others
Other classifications of complications	Diabetes mellitus, gastrointestinal disorder, osteoporosis, malignant tumour, collagen disorder, others
Medical history	Absent, present, unknown, not described
Detailed classifications of medical history	tuberculosis, bacterial bronchitis, nontuberculous mycobacterial infection, aplastic anaemia, pancytopenia, malignant tumour, others
Previously used drug/previous treatment	Absent, present, unknown, not described
Classification of biological preparation as previously used drug/previous treatment	Adalimumab, infliximab, others
Classification of drugs other than biological preparation as previously used drug/previous treatment	Biological preparation, aminosalicylic acid preparation, steroid, immunomodulative drug, antibiotic, other previously used drug, operation, other previous treatment
Concomitant drug	Absent, present, unknown, not described
Detailed classification of concomitant drugs	Aminosalicylic acid preparation, oral adrenocortical steroid, immunomodulative drug, immunosuppressive drug, enteral nutrient, colchicine, others
Combination therapy	Absent, present, unknown, not described
Detailed classification of combination therapy	Operation, others
Endoscopy	Absent, present, unknown, not described

data	Method of dividing hierarchy
Detailed classifications of endoscopy	Ileocecum, colon, esophagus, others
Level of improvement in endoscopy findings	Remission or scar, shrinkage, no change, aggravation, not assessed
Evaluation of gastrointestinal symptoms	
0,1,2,3,4
 
0: No symptom
 
1: There was symptom in last 2 weeks but daily living activities were rarely disturbed.
 
2: There was symptom in last 2 weeks and daily living activities were slightly disturbed.
 
3: There was symptom in last 2 weeks and daily living activities were disturbed.
 
4: There was symptom in last 2 weeks and daily living activities were severely disturbed.

Detailed classifications of gastrointestinal symptoms	Abdominal pain, diarrhoea, others (including bloating, abdominal tenderness, haemorrhage)
Self-administration	Absent, present
Self-administration error	Absent, present, unknown, not described
Drug used after the discontinuation of this drug	Absent, present, unknown, not described
Detailed classifications of drug used after the discontinuation of this drug	Aminosalicylic acid preparation, steroid, immunomodulative drug, biological preparation, other drug
Level of overall improvement	Significant improvement, improvement, ineffective
Detailed classifications of level of overall improvement for patients with improvement or higher level of improvement	Significant improvement, improvement

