	
identified, the date described as the last date of the treatment should be employed.
 
[3] When there is no description in the section for the last date of the third or subsequent treatment or there is a check mark in “Ongoing” box so that the last date of the treatment cannot be identified, following rules are applied.
 
 
● When the patients are included in the last period in the volume: The date should be complemented by the last follow-up date for relevant volume or a date obtained by subtracting 1 day from start date of the subsequent treatment, which is earlier.
 
● When the patients are included in not last period in the volume: The date should be complemented by a date obtained by subtracting 1 day from the start date of the subsequent treatment with this drug.
 
 
The last follow-up date should be defined as follows:
 
 
• The initial volume: Start date of the treatment with this drug + 364 days
 
• The second volume: Start date of the treatment with this drug + 728 days
 
• The second volume: Start date of the treatment with this drug + 1092 days
 
 
[4] When there is description in the section for the last date of the third or subsequent treatment but the date is incomplete so that the last date of the treatment cannot be identified, following rules are applied.
 
 
● When the date include year and month, but date is unknown: The date should be complemented by the last date of relevant month.
 
● When the date include year, but month and date is unknown: The date should be complemented by the last date in the last month of relevant year. In addition, when records in the subsequent treatment are created and the start date of the subsequent treatment is earlier than the complemented last date in the last month of the relevant year, the last date of the treatment should be complemented by the date obtained by subtracting 1 day from the start date of the subsequent treatment.
 
 
However, if description in the last date of the treatment in the records for which last date of the treatment was complemented according to above rules and there is a check mark in “Ongoing” box, following rules are applied:
 
 
● When the described last date of the treatment is later than the last date complemented according to above rules, the date complemented should be employed as the last date of the final treatment of this drug.
 
● When the described last date of the treatment is earlier than the last date complemented according to above rules, the date described should be employed as the last
 

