
Name of data	Derivation and calculation method
	
date of the final treatment of this drug.
 
In addition, the last date identified according to above rule is later than the last follow-up date, the last follow-up date should be employed as the last date of the final treatment with this drug.

Days to the last date of the final treatment with this drug	
The last date of the final treatment with this drug - the start date of the initial treatment with this drug + 1

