## 12. Handling of data at test and evaluation

### 12.1. Time of evaluation of administration status of this drug

Time Allowance at evaluation when the start date of the initial administration of this drug is defined as 1 is as follows:

Time of evaluation	Time Allowance(Day)
At least 0 week and shorter than 4 weeks	1-28
At least 4 week and shorter than 12 weeks	29-84
At least 12 week and shorter than 24 weeks	85-168
At least 24 week and shorter than 52 weeks	169-364
At least 52 weeks and shorter than 104 weeks	365-728
At least 104 weeks and shorter than 156 weeks	729-1093

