### 12.2. Time of evaluation of occurrence status of adverse reactions

Time Allowance at evaluation when the start date of the initial administration of this drug is defined as 1 is as follows:

Time of evaluation	Time Allowance(Day)
Within 4 weeks after the administration start	1-28
From 4 weeks within 12 weeks after the administration start	29-84
From 12 weeks within 24 weeks after the administration start	85-168
From 24 weeks within 52 weeks after the administration start	169-364
From 52 weeks within 104 weeks after the administration start	365-728
From 104 weeks within 156 weeks after the administration start	729-1092
Patients who received this drug for over156 weeks	1093-

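### The top administration-duration class in SAP sections 11 and 12.1 ends one day too late, so a full 156-week exposure (1093 days) is labelled as under 156 weeks

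*SAP*

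**What the plan says.** Section 11 sorts administration duration into six classes plus unknown, with the note "When the start date of the administration is defined as 1". The last two numeric classes are "at least 52 weeks and shorter than 104 weeks (365-728 days") and "at least 104 week and shorter than 156 weeks (729-1093 days"). Section 12.1 has the same six windows; its last row, "At least 104 weeks and shorter than 156 weeks", also covers days 729-1093, and nothing follows it. Table 1.6 counts patients by the section 12.1 windows, in both the safety and the efficacy population.

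Section 10.1 defines the quantity being classified: "The last date of the final treatment with this drug - the start date of the initial treatment with this drug + 1". For the 156-week patients the last follow-up date is "Start date of the treatment with this drug + 1092 days", and a last date that falls later is replaced by it. That line carries the wrong volume label ("The second volume: Start date of the treatment with this drug + 1092 days"), but the record rule in the same entry ties + 1092 to patients who started by August 15, 2013, the 156-week cohort.

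Section 12.2 gives windows for the onset of adverse reactions. There "From 104 weeks within 156 weeks after the administration start" is days 729-1092, and a separate open window starts at day 1093. Table 2.7 uses these windows.

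**The concern.** The label of the top class and its day bound cannot both be right. An error of one day in a wide class would usually be harmless, but day 1093 is not an ordinary day on this scale: under the SAP's cap and formula it is where every fully treated 156-week patient falls. The distribution would describe these patients as not having reached 156 weeks, while the 52- and 104-week cohorts get the correct label at the matching point. Section 3.1 says that the results feed the survey report and the reassessment application, so readers will take the row label at face value.

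**Working it through.** **Inputs.** Class bounds: sections 11 and 12.1. Day numbering (start = day 1): section 11. Duration formula and last follow-up dates (start + 364, + 728, + 1092): section 10.1. Discontinuation cut-off for the 156-week cohort (last date before start + 1064): section 10.1. Onset windows: section 12.2. Table 2.7 denominators: section 13.2.

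**Step 1: reproduce the bounds.** With the start as day 1, a class of under W weeks ends on day 7 × W.

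| W (weeks) | 7 × W | Printed upper bound |
|---|---|---|
| 4 | 28 | 28 |
| 12 | 84 | 84 |
| 24 | 168 | 168 |
| 52 | 364 | 364 |
| 104 | 728 | 728 |
| 156 | 1092 | 1093 |

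Five of six agree; the last does not. Counting the start as day 0 would shift all six bounds, so it does not explain the difference. The widths show the same thing: 728 − 365 + 1 = 364 days for the fifth class, 1093 − 729 + 1 = 365 for the sixth, although each spans 52 weeks.

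**Step 2: duration at full exposure.** Duration = (start + offset) − start + 1 = offset + 1.

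| Cohort | Offset | Full duration | Class in 11 and 12.1 | Window by day in 12.2 |
|---|---|---|---|---|
| 52 weeks | 364 | 365 | 52 to under 104 weeks | 365-728 |
| 104 weeks | 728 | 729 | 104 to under 156 weeks | 729-1092 |
| 156 weeks | 1092 | 1093 | 104 to under 156 weeks | 1093 onward |

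The printed 1093 equals 1092 + 1, the largest duration the cap allows. Only the third row gets a label that is false for the patients in it.

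**Step 3: who is affected.** A 156-week patient counts as not discontinued from a last date of start + 1064, which is 1064 + 1 = 1065 days. Durations of 1065 to 1092 days are under or at the 1092-day limit and are correctly labelled. Only the value 1093 is wrong.

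**Step 4: what Table 2.7 shows.** Its notes assign 156-week patients who did not discontinue to the window beyond 156 weeks. A discontinued patient counts until 28 days after the last date, at the latest start + 1063 + 28 = start + 1091, which is day 1092. So none enters the window from day 1093, and its denominator is the set of 156-week patients in the safety population who did not discontinue.

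**The case against.** The best defence is that nobody is lost. The cap makes 1093 the largest possible value, so the closed top class holds every long-exposed patient once; the bound may have been stretched on purpose to achieve this. That explains the number but leaves the label false.

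It is also fair that section 12.2 is not a strict template. It classifies onset of reactions, the safety window runs to start + 1120, and so it needs an open last window that duration does not need. Even so, both sections number days the same way and share every lower bound, and only one of them puts day 1093 beyond 156 weeks.

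Three stronger readings are tempting, and the SAP does not support them:

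- A reader might infer that Table 1.6 would report zero patients with full exposure. It has no row for 156 weeks, so it reports no zero, and its summary statistics of days would show a maximum of 1093 if any patient reached it.
- A reader might infer that the number with three years of exposure is lost. Table 2.7 gives the 156-week patients who did not discontinue as a denominator (a slightly wider group, 1065-1093 days), and the patient list in Table 1.4 carries days of administration.
- A reader might infer that 104-week completers are misplaced because they share the class. At 729 days they have passed 104 weeks (728 days); their label is true, and they stay in that class after the correction.

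**Conclusion.** The point holds as a one-day error in the top class of sections 11 and 12.1. It gives a false exposure label to every patient with exactly 1093 days, and it conflicts with section 12.2. The conclusion rests on the cap at start + 1092 and the added day being applied as written.

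The reach is limited to the duration distribution in Table 1.6. Analyses 2.9 and 3.4 list days to the last administration as a factor; they are affected only if they use these classes, which the SAP does not state. No sample size or significance level changes. The number of patients concerned is not known, since the SAP leaves the survey size undecided and gives no completion rate. It is worth correcting because it is a wrong category in a reported table and costs almost nothing to put right.

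**What to change.** In sections 11 and 12.1, change the upper bound of the top class from 1093 to 1092 days and add a class for 156 weeks or longer (1093 days). This agrees with the 1092/1093 split in section 12.2. If analyses 2.9 and 3.4 group duration by section 11, the new class should carry through to them.

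The cost is one changed bound and one added row in each of two SAP tables, with the matching row in Table 1.6. No new data are needed. A cross-tabulation of duration by follow-up cohort would be optional presentation and is not needed to correct the error.

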## 12. Handling of data at test and evaluation

### 12.1. Time of evaluation of administration status of this drug

Time Allowance at evaluation when the start date of the initial administration of this drug is defined as 1 is as follows:

Time of evaluation	Time Allowance(Day)
At least 0 week and shorter than 4 weeks	1-28
At least 4 week and shorter than 12 weeks	29-84
At least 12 week and shorter than 24 weeks	85-168
At least 24 week and shorter than 52 weeks	169-364
At least 52 weeks and shorter than 104 weeks	365-728
At least 104 weeks and shorter than 156 weeks	729-1093

### 12.2. Time of evaluation of occurrence status of adverse reactions

Time Allowance at evaluation when the start date of the initial administration of this drug is defined as 1 is as follows:

Time of evaluation	Time Allowance(Day)
Within 4 weeks after the administration start	1-28
From 4 weeks within 12 weeks after the administration start	29-84
From 12 weeks within 24 weeks after the administration start	85-168
From 24 weeks within 52 weeks after the administration start	169-364
From 52 weeks within 104 weeks after the administration start	365-728
From 104 weeks within 156 weeks after the administration start	729-1092
Patients who received this drug for over156 weeks	1093-

### 12.3. Time of evaluation of level of overall improvement

At the final follow-up: The evaluation at the last follow-up in which level of improvement for each patient was assessed as “1. significant improvement”, “2. improvement”, or “3. ineffective” is employed.

Patients who discontinued the administration of this drug should be followed-up until 14 days after the last date of the final administration of this drug, and within this period, the evaluation at the last follow-up in which level of improvement was assessed as “1. significant improvement”, “2. improvement”, or “3. ineffective” is employed.

In patients in whom follow-up was continued, the evaluation for following period should be included in analysis: Time Allowance at evaluation when the start date of the initial administration of this drug is defined as 1 is as follows:

Time of evaluation	Time Allowance(Day)
The last follow-up (patients who were continuously followed up)	

Patients who were followed up for 52 weeks: the start date of the initial administration of this drug + 37 (52 weeks + 14 days)

Time of evaluation	Time Allowance(Day)
	
 
Patients who were followed up for 104 weeks: the start date of the initial administration of this drug + 756 (104 weeks + 28 days)
 
Patients who were followed up for 156 weeks: the start date of the initial administration of this drug + 1120 (156 weeks + 28 days)
 

12.4. Time of evaluation of rate of clinical improvement, rate of complete remission, and level of improvement in endoscopy findings

Time Allowance at evaluation when the start date of the initial administration of this drug is defined as 1 is as follows:

Time of evaluation	Time Allowance(Day)
Within 24 weeks after the administration start	1-168
At least 24 weeks and within 52 weeks after the administration start	169-364
At least 52 weeks and within 76 weeks after the administration start	365-532
At least 76 weeks and within 104 weeks after the administration start	533-728
At least 104 weeks and within 128 weeks after the administration start	729-896
At least 128 weeks and within 160 weeks after the administration start	897-1121

Data of rate of clinical improvement and complete remission with evaluation of endoscopy findings obtained within Time allowance and evaluation of gastrointestinal symptoms within 4 weeks before and after the date of endoscopy implementation should be employed.

If there are multiple measurements during the same period, the measurement obtained on the latest date should be employed.

